8.1. General Considerations

Objectives for Part C of AACH will be addressed with summaries of clinical, imaging, and biomarker data. Data collected from the feeder study from which the participant came, and data from the first on-site visit from Part A will be aggregated with data from Part C to allow for display of longitudinal changes. For comparative purposes, subjects that participate in Part B will also be displayed, with their feeder study, first Part A on-site visit, and Visit 1 from Part B (pre-treatment) aggregated in a similar fashion.

Unless otherwise specified, baseline for clinical, imaging, and biomarker endpoints will be defined as the last observation prior to study drug initiation from the feeder study. When change from baseline is assessed, patients will be included in the analysis only if both a baseline and a Part C measure are available.

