To assess long-term effect of donanemab on brain amyloid deposition, brain tau deposition, blood-based biomarkers, and clinical progression of AD in participants who received donanemab in the originating study	Change in the following endpoints from baseline in the originating study through $\geq 52$ weeks after the participant's last double-blind visit in the originating study, using Part C assessments: 
 
• Amyloid plaque deposition as measured by florbetapir F 18 PET scan
 
• Tau deposition as measured by flortaucipir F 18 PET scan
 
• NfL
 
• P-tau
 
• A<math>\beta</math>
 
• MMSE score
 
• ADAS-Cog13 score
 
• iADRS score
 
• ADCS-iADL score
 
• CDR-SB
 

To assess the effect of donanemab on blood-based biomarkers	Change from baseline to Week 72 in the following blood-based biomarkers in Part B: 
 
• NfL
 
• P-tau
 
• A<math>\beta</math>
 

To evaluate the reliability of VTC compared with on-site administered cognitive and functional measures	
The intraclass correlation between VTC and on-site assessment for PAIR 2 and PAIR 3 compared with intraclass correlation of PAIR 1 for
 
 
• ADAS-Cog13
 
• ADCS-ADL
 
• MMSE
 
• CDR-SB
 

To assess clinical progression as measured by VTC versus F2F-administered cognitive and functional measures	
Change from V602 to V608 as measured by
 
 
• ADAS-Cog13
 
• ADCS-ADL
 
• MMSE
 
• CDR-SB
 

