**Part C** has an exploration scientific rationale, examining participants who previously received donanemab, but are no longer receiving donanemab following the completion of the originating clinical trial. This exploratory objective is directed toward assessing long-term effect of donanemab on brain amyloid deposition, brain tau deposition, and clinical progression of AD in participants over the interval period when they no longer receive donanemab.

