### 9.4. Statistical Analyses

#### 9.4.1. General Considerations

Statistical analysis of this study will be the responsibility of the sponsor or its designee.

Unless otherwise noted, statistical tests will be conducted at a 2-sided alpha level of 0.05 and 95% confidence intervals will be displayed as 2-sided.

No adjustments for multiple comparisons are planned.

All analyses involving calculation of ICCs will be limited to the Efficacy Evaluable population, requiring participants to contribute complete pairs of on-site and remote clinical assessments to be included. The ICC will be calculated as 2-way mixed-effect model looking for absolute agreement across multiple raters, with raters defined as on-site assessment and VTC assessment. See Section 9.4.2 below and the SAP for further specification of the analysis.

If either ADAS-Cog13 or ADCS-iADL is missing, iADRS score will be considered missing.

Baseline definitions are dependent on the quantity being assessed. For TE safety analyses, only participants who have both a baseline observation and a postbaseline observation will be included in the analysis for each analyte or parameter, respectively. The SAP will define baselines where needed.

A database lock is expected to occur after all randomized participants have completed participation in Part A of the study. Analyses related to the validation of remote assessments compared to on-site assessments will be conducted. As no IP is administered during Part A, safety analyses will be limited.

Any change to the data analysis methods described in the protocol will require an amendment only if it changes a principle feature of the protocol. Any other change made to the data analysis methods described in the protocol, and the justification for making the change, will be described

in the SAP and the clinical study report. Additional exploratory analyses of the data will be conducted as deemed appropriate.

The SAP will be finalized prior to first participant visit and will include a more technical and detailed description of the statistical analyses described in these sections.

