For participants in Part C of the study, the interest is whether the changes in brain amyloid deposition, brain tau deposition, and clinical progression of AD for participants who received donanemab in the originating study are maintained after donanemab treatment is removed. For each of these endpoints, change from the last observation of the originating study will be fit using an ANCOVA model including terms for age, years of education, and presence/absence of anti-dementia drugs. Observed case analyses will also be presented.

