7.5. Efficacy Scales	12
7.6. Safety Analyses	12
7.6.1. Adverse Events	12
7.6.2. Clinical Laboratory Evaluations	13
7.6.3. Electrocardiogram Parameters	14
7.6.4. Vital Signs and Weight	15
7.6.5. Columbia Suicide Severity Rating Scale (C-SSRS)	15
7.6.6. Immunogenicity	15
7.6.7. Amyloid-Related Imagine Abnormalities (ARIA)	16
7.7. Subgroup Analyses	16
8. Part C Analyses	17

8.1. General Considerations	17
8.2. Adjustments for Covariates	17
8.3. Handling of Dropouts or Missing Data	17
8.4. Patient Demographics.....	17
8.5. Time Between Clinical, Imaging, and Biomarker Assessments	18
8.6. Clinical Outcomes	18
8.7. PET Imaging Outcomes	18
8.8. Plasma Biomarker Outcomes	19
9. References	20
10. Appendices	21

3. Revision History

The original version of the statistical analysis plan was approved 15-Oct-2018, prior to first patient visit. Version 2 included modifications to the description of Part C analyses that incorporate data across both the feeder study and this follow-on study. Additionally, version 2 updates the feeder studies to include I5T-MC-AACC.

4. Study Objectives

Table AACH.4.1. Objectives and Endpoints

Primary Objective	Primary Endpoint
Part A To evaluate the reliability of VTC compared with on-site administered cognitive and functional measures	The intraclass correlation between VTC and on-site assessment for PAIR 1 for 
 • ADAS-Cog₁₃ • ADCS-ADL • MMSE • CDR-SB
Part B To evaluate safety and tolerability of donanemab	Standard safety assessments in Part B: 
 • Spontaneously reported AEs • Clinical laboratory tests • Vital sign and body weight measurements • 12-lead ECGs • Physical and neurological examinations MRI (ARIA and emergent radiological findings) Infusion-related reactions C-SSRS
Secondary Objectives	Secondary Endpoints
To assess the effect of donanemab on clinical progression in participants with symptomatic AD	Change from baseline up to Week 72 as measured in Part B by: 
 • MMSE score • ADAS-Cog₁₃ score • iADRS score • ADCS-iADL score • CDR-SB
To assess the effect of donanemab on brain amyloid deposition	Change in brain amyloid plaque deposition from baseline at Week 36 of Part B as measured by florbetapir F 18 PET scan
To assess the effect of donanemab on brain region volumes	Change in volumetric MRI measures from baseline to Week 72 in Part B

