8.7. PET Imaging Outcomes

Longitudinal assessment across the feeder study and study AACH will be summarized for Part C participants for florbetapir PET and flortaucipir PET results. Change from baseline to each scheduled collection of these measures during the feeder study and to the Part C assessment of study AACH will be modelled with an analysis of covariance (ANCOVA) model with factors for baseline PET result, baseline age, years of education, and presence/absence of anti-dementia medications (yes/no).

Additionally, each of these outcomes will be analyzed on an annualized basis. Time from the baseline assessment to each post-baseline assessment will be determined and divided by 365 to derive a change per year value. These values will be modelled using the same ANCOVA analysis specified above.

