8.8. Plasma Biomarker Outcomes

Longitudinal assessment across the feeder study and study AACH will be summarized for Part C participants for Ptau-217 and neurofilament light chain (NfL) protein. Change from baseline to each scheduled collection of these measures during the feeder study and to the Part C assessment of study AACH will be modelled with an analysis of covariance (ANCOVA) model with factors for baseline value, baseline age, and AACG treatment group. For both of these biomarkers, changes on the original scale and the log-transformed scale will be displayed.

For comparison purposes to an untreated participant population, change from baseline to each of the same visits will be shown for AACH subjects that participated in Part B of AACH, with the exception that the Part C assessment would be replaced by the Part B Visit 1 (prior to treatment) assessment.

Additionally, each of these outcomes will be analyzed on an annualized basis. Time from the baseline assessment to each post-baseline assessment will be determined and divided by 365 to derive a factor to be multiplied by the observed change, resulting in a change per year value. These values will be modelled using the same ANCOVA analysis specified above.

9. References

Mcgraw, Kenneth & Wong, S.P.. (1996). Forming Inferences About Some Intraclass Correlation Coefficients. *Psychological Methods*. 1. 30-46. 10.1037/1082-989X.1.1.30.

10. Appendices

Signature Page for VV-CLIN-076528 v1.0

Approval

PPD

13-Dec-2022 15:02:05 GMT+0000

Signature Page for VV-CLIN-076528 v1.0

Approved on 13 Dec 2022 GMT

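### Part C: SAP 8.8 multiplies where a change per year needs division, and the off-drug ANCOVA planned in protocol 9.4.4 is neither carried into the SAP nor explained

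*SAP*

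**What the plan says.** **Annualisation.** SAP 8.8 (plasma P-tau217 and NfL) takes the time from baseline, "divided by 365 to derive a factor to be multiplied by the observed change, resulting in a change per year value". SAP 8.7 (PET) says only that time is "divided by 365 to derive a change per year value", and 8.6 (clinical outcomes) has the same wording. Neither says how the observed change enters the calculation.

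**Reference point.** SAP 8.1 sets the Part C default: "baseline for clinical, imaging, and biomarker endpoints will be defined as the last observation prior to study drug initiation from the feeder study". Sections 8.6 to 8.8 name no other reference point. Sections 8.6 and 8.7 model change from that baseline to each scheduled feeder visit and to the Part C visit (Visit 201); 8.6 also includes the first on-site visit of Part A.

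The protocol gives two reference points. Section 3 lists the Part C endpoints as "Change in the following endpoints from baseline in the originating study". Section 9.4.4 asks whether changes in amyloid, tau and clinical progression hold up once donanemab is stopped, and there "change from the last observation of the originating study will be fit using an ANCOVA model", adjusted for age, education and anti-dementia drug use. Section 4.2 directs the Part C objective to effects "in participants over the interval period when they no longer receive donanemab".

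On changes of method, protocol 9.4.1 names both the SAP and the study report as the place to record them: "Any other change made to the data analysis methods described in the protocol, and the justification for making the change, will be described". The SAP revision history records that "Version 2 included modifications to the description of Part C analyses" so as to bring in data from both studies. It does not mention the 9.4.4 ANCOVA.

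**Untreated comparison.** In SAP 8.6 and 8.8, participants who went on to Part B serve as the untreated group, with their pre-treatment Visit 1 standing where Visit 201 would be. SAP 8.5 summarises the weeks from feeder baseline to each assessment.

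**The concern.** Multiplying a change by elapsed years gives change times years, not change per year. A programmer who follows 8.8 to the letter would produce plasma rates that are too small before one year and too large after it, so a perfectly steady change would look as if it were accelerating. Sections 8.6 and 8.7 do not help, because they leave the step out.

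The question in protocol 9.4.4 and 4.2 concerns the period off drug. A change from pre-treatment baseline to Visit 201 adds the on-drug change to the off-drug change. If the 9.4.4 ANCOVA is not run, the maintenance question has no specified estimate with its own measure of precision.

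In the untreated comparison, Visit 1 and Visit 201 follow different timing rules. Part of any unannualised difference between the groups could therefore be elapsed time alone.

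**Working it through.** The documents give no sample size, power or other figure for Part C, so there is nothing of the plan's own to reproduce. The checks are units, calendar arithmetic and a side-by-side reading.

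**1. SAP 8.8 annualisation**

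- As written: change × (days/365).
- A rate per year: change ÷ (days/365).
- Ratio of the first to the second: (days/365)², that is, years squared.

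| Weeks from feeder baseline | days/365 | Reported, if the true rate is 1.0 per year |
|---|---|---|
| 24 | 168/365 = 0.460 | 0.21 |
| 76 | 532/365 = 1.458 | 2.12 |
| 152 | 1064/365 = 2.915 | 8.50 |

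The two formulas agree only near one year (at week 52, 364/365 squared = 0.99). Feeder length is not in the documents. Weeks 76 and 152 are the earliest Visit 201 (52 weeks after the last double-blind visit) for assumed feeder lengths of 24 and 100 weeks.

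**2. Off-drug change**

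Let Y0, YL and YV be the values at feeder baseline, at the last feeder observation and at Visit 201.

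- Protocol Section 3 and SAP 8.1, 8.6 and 8.7 use YV − Y0.
- Protocol 9.4.4 uses YV − YL.
- SAP 8.6 and 8.7 also model YL − Y0, because they cover every scheduled feeder visit.
- (YV − Y0) − (YL − Y0) = YV − YL, so subtracting two planned estimates approximates the 9.4.4 quantity. SAP 8.1 requires a baseline and a Part C measure for change analyses, so largely the same people contribute to both.
- The variance of that difference is Var(YV − Y0) + Var(YL − Y0) − 2Cov(YV − Y0, YL − Y0). The covariance is in no specified output, so the uncertainty cannot be recovered from the two estimates.

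Protocol 9.4.4 names amyloid, tau and clinical progression in this analysis, not blood biomarkers. The gap therefore lies in SAP 8.6 and 8.7.

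**3. Timing of Visit 1 and Visit 201**

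Inputs from the protocol's Schedule of Activities (footnotes and Part C table): Visit 602 at least 30 days after the last double-blind visit, Part A visits 4 weeks apart, at least 4 weeks from Part A to Visit 1, and Visit 201 at 52 weeks or later.

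- Earliest Visit 1, one pair: 30 + 28 + 28 = 86 days = 12.3 weeks.
- Earliest Visit 1, three pairs: 30 + 140 + 28 = 198 days = 28.3 weeks.
- Gap to the earliest Visit 201: 52 − 12.3 = 39.7 weeks, or 52 − 28.3 = 23.7 weeks.

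With equal linear change in both groups and assumed feeder length L, elapsed time alone gives the Part C group (L + 52)/(L + V1) times the comparator's change, where V1 is weeks from the last double-blind visit to Visit 1:

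| Visit 1 (weeks) | L = 24 | L = 100 |
|---|---|---|
| 12.3 | 76/36.3 = 2.09 | 152/112.3 = 1.35 |
| 28.3 | 76/52.3 = 1.45 | 152/128.3 = 1.18 |
| 52 | 1.00 | 1.00 |
| 60 | 76/84 = 0.90 | 152/160 = 0.95 |

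The last row is possible: neither visit has a latest date, and footnote b foresees a Visit 1 more than 12 months after the last feeder MRI.

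**The case against.** **The SAP follows the protocol's endpoint table.** This stands. Section 3 defines the Part C endpoints from originating-study baseline, and SAP 8.1 agrees with it. A reader might infer that the SAP contradicts the protocol, or that 9.4.4 should be the main analysis. The documents support neither: the protocol is inconsistent with itself, and nothing in it ranks one reference point above the other.

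**The off-drug information is not lost.** This stands too. A reader might infer that the planned outputs only mix on-drug and off-drug change. They do not: 8.6 and 8.7 show change at each feeder visit and at Visit 201, and 8.6 adds a Part A visit in between. What is missing is a direct estimate of the off-drug change and its precision.

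**The missing justification is only partly checkable.** Protocol 9.4.1 also places it in the clinical study report, which is not available here. What can be said is that the SAP gives none.

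**The 8.8 error is unlikely to be programmed.** Probably so, since the output is described as a change per year. It concerns two plasma markers in an additional analysis. It is still a wrong instruction in an approved plan.

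**The timing point is largely covered.** Mostly true. SAP 8.5 summarises elapsed weeks, and 8.6 and 8.8 plan annualised results, which deal with unequal time if change is linear and the rate is computed correctly. For clinical outcomes the first Part A on-site visit already shows both groups under the same timing rule. A reader might infer from the ratios of 1.18 to 2.09 that the display is biased against donanemab. They rest on earliest dates, an assumed feeder length and linear change, and with a later Visit 1 the ratio reaches 1.00 or falls below it.

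**Conclusion.** Three conclusions hold, in this order.

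1. SAP 8.8 is wrong as written. If implemented literally, its rates are off by years squared, whatever the biomarker. It is probably a drafting slip. Sections 8.6 and 8.7 are incomplete rather than wrong.
2. The protocol gives two reference points for Part C. The SAP adopts the one in Section 3 and is silent on the ANCOVA in 9.4.4, with no reason in its revision history. The consequence is limited to the absence of a direct estimate, with its uncertainty, of amyloid, tau and clinical change off drug.
3. The unannualised comparison of Visit 1 with Visit 201 is not time-matched by design. The illustrative ratio runs from 0.90 to 2.09, so neither the direction nor the size of any effect is established. This is a labelling matter.

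The years-squared factor needs no assumption; placing Visit 201 at weeks 76 to 152 assumes a feeder length of 24 to 100 weeks and the earliest permitted visit. Part C is exploratory and protocol 9.1 states no hypothesis for it, so this should be corrected but with modest priority.

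**What to change.** 1. In SAP 8.8, divide the observed change by (days/365). Write the same division in 8.6 and 8.7.
2. Reconcile protocol Section 3 with 9.4.4. Then either add the 9.4.4 ANCOVA of change from the last originating-study observation to Visit 201 to SAP 8.6 and 8.7, alongside change from baseline and without ranking one above the other, or state in the SAP why it is dropped.
3. In the untreated comparisons of SAP 8.6 and 8.8, label the unannualised Visit 1 versus Visit 201 contrast as not time-matched and print the elapsed weeks from SAP 8.5 beside it. For clinical outcomes, point the reader to the first Part A on-site visit as the common time point.

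The cost is one protocol clarification, a few lines in the SAP and one extra model per clinical and PET outcome. No new data are needed, because SAP 8.1 already combines feeder and Part C data.

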8.2. Adjustments for Covariates

Models for each of the clinical, imaging, and biomarker endpoints are specified in the relevant sections below.

8.3. Handling of Dropouts or Missing Data

All total and subscale scores for clinical outcomes measures will be derived from individual items. If any of the individual items are missing or unknown, every effort will be made to obtain the score for the missing item(s). Similar to Part A analyses, if any item is missing, any total or sum involving that item will be considered missing.

For fluid biomarkers, samples that were not collected for any reason as well as samples that were not quantifiable (i.e. below the limit of quantification) will be considered missing for analysis purposes.

For PET imaging, scans that were not collected for any reason as well as scans that were not quantifiable will be considered missing for analysis purposes.

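### Setting below-LOQ plasma biomarker results to missing can shrink Part C changes in Ptau-217 and NfL toward no change, if such results are not rare and a real change exists

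*SAP*

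**What the plan says.** SAP 8.3 covers two kinds of fluid-biomarker sample in one sentence and treats them alike: those not collected for any reason, and those below the limit. Of the second kind it says that "samples that were not quantifiable (i.e. below the limit of quantification) will be considered missing for analysis purposes".

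SAP 8.1 adds a complete-case rule for change from baseline: "patients will be included in the analysis only if both a baseline and a Part C measure are available". A below-LOQ result at either time therefore removes the participant.

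SAP 8.8 applies this to "Part C participants for Ptau-217 and neurofilament light chain (NfL) protein". Change is modelled by ANCOVA with "factors for baseline value, baseline age, and AACG treatment group", and "changes on the original scale and the log-transformed scale will be displayed". For an untreated comparison, "change from baseline to each of the same visits will be shown for AACH subjects that participated in Part B of AACH", with Part B Visit 1 before treatment standing in for the Part C visit.

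SAP 8.3 and 8.8 contain no censored-data method, substitution rule, below-LOQ count or sensitivity analysis. For people previously treated with donanemab, blood-based biomarkers at Part C belong to a tertiary/exploratory objective (Protocol Section 3): "To assess long-term effect of donanemab on brain amyloid deposition, brain tau deposition, blood-based biomarkers, and clinical progression of AD in participants".

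**The concern.** A below-LOQ result is an observation: the value lies somewhere under a known limit. An uncollected sample carries no such information. Treating the two alike means that deletion depends on the outcome value, so the missingness is informative by construction. Adjusting for baseline does not repair it, because the selection is on the outcome.

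At stake is what Part C can say about plasma markers after at least 52 weeks off drug (Protocol 2.1). If a marker is still reduced, the deleted participants are those with the lowest follow-up values, and the estimate moves toward no change. That could be misread as loss of effect. Because no below-LOQ count is planned, the reader of the results could not tell whether this had happened.

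**Working it through.** **Nothing to reproduce.** The documents state no sample size, power, LLOQ, below-LOQ rate or expected change for the Part C biomarkers. The 81% power in Protocol 9.2 concerns the Part A ICC.

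**Inputs from the SAP.** Participants with a below-LOQ value at baseline or follow-up are dropped (8.3 with 8.1). The model is an ANCOVA adjusted for baseline with a group term, here on the log scale (8.8).

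**Assumed inputs.** Log SD 0.4; correlation r between baseline and follow-up of 0.6, 0.8 or 0.9; no change in untreated participants; true treated change of -20% or -40% (also 0% and +10%); a fraction p of treated follow-up values below LOQ of 1, 5, 10 or 20%.

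**Set-up.** Log baseline B ~ N(0, 0.4²). Log follow-up Y = r·B + 0.4·√(1 − r²)·e + d·T, where e is standard normal, T = 1 if treated, and d = ln(1 + true change). The limit is L = d + 0.4·z_p.

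Example for -20% and p = 5%: L = -0.223 + 0.4 × (-1.645) = -0.881. In the untreated, Φ(-0.881/0.4) = Φ(-2.20) = 1.4% of values fall below the same limit. One limit for everyone therefore removes unequal fractions once the groups differ.

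**ANCOVA difference under the SAP rule** (simulated, 1,000,000 per group; separate runs agree within about 0.2 points):

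| True change | p | r = 0.9 | r = 0.8 | r = 0.6 |
|---|---|---|---|---|
| -20% | 1% | -19.9 | -19.7 | -19.6 |
| -20% | 5% | -19.5 | -19.1 | -18.5 |
| -20% | 10% | -19.1 | -18.4 | -17.4 |
| -20% | 20% | -18.3 | -17.3 | -15.8 |
| -40% | 5% | -39.5 | -39.0 | -38.3 |
| -40% | 10% | -39.0 | -38.3 | -37.0 |
| -40% | 20% | -38.2 | -36.8 | -34.7 |

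- At 0% below LOQ there is no bias.
- With no true change in either group there is no bias at any p, because losses at baseline and follow-up balance.
- With a true +10% (r = 0.8), the rule gives about +9.1% at p = 5% and +8.0% at p = 20%. It shrinks increases as well.
- At p = 10% and r = 0.8, the rule drops about 11% of treated and 5% of untreated participants for a true -20%, and 10% against 0.9% for a true -40%.

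**In SD units.** Bias = [ln(1 + estimate) − ln(1 + true)]/0.4. For -20%, p = 20%, r = 0.6: [ln 0.842 − ln 0.8]/0.4 = (-0.172 + 0.223)/0.4 = 0.13. At r = 0.9: [ln 0.817 − ln 0.8]/0.4 = 0.05. At p = 5% the range is about 0.02 (r = 0.9) to 0.05 (r = 0.6).

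**Check of remedies.** A Tobit ANCOVA on the log scale treated below-LOQ follow-up values as left-censored at L and left out below-LOQ baselines. It came within 0.1 point of the complete-data estimate for the same participants in every scenario. Substituting LLOQ/2 for a true -20% (r = 0.8) gave about -21.5, -22.6 and -24.1% at p = 5, 10 and 20%.

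**The case against.** The strongest reply is that nothing shows the rule will matter. The documents give no below-LOQ rate and no expected change. Participants are at least 52 weeks off drug, so a persisting reduction is itself the open question. The endpoint is exploratory, Part C objectives are met mainly by summaries, and no Part C biomarker hypothesis or power is stated. The rule is explicit, prespecified, and covers feeder-study baselines and untreated comparators too. All of this stands, and it limits both the size and the priority of the point.

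Two parts do not stand. A rule applied equally does not remove participants equally once the groups differ, as the drop fractions show. It might also be said that a Tobit model leaves a below-LOQ baseline unhandled. Excluding those participants selects on a covariate in the model, not on the outcome. With the linear model right, the group difference stays unbiased, and the check above bears this out.

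A reader might also size the problem by the shift in the mean of a truncated normal, φ(z_p)/(1 − p): 0.11 SD at 5% and 0.35 SD at 20%. That is the shift of one visit's mean. The SAP analyses baseline-adjusted change in participants with both values, and the bias there is 0.02 to 0.05 SD and 0.05 to 0.13 SD for a true -20%.

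**Conclusion.** The point holds in conditional form. The rule makes deletion depend on the biomarker value, and nothing else in the SAP corrects for it. If below-LOQ results are not rare and a marker truly changes, Part C changes and group differences are pulled toward no change. For a true -20% the loss is about 0.5 to 1.5 percentage points at 5% below LOQ and 1.7 to 4.2 points at 20%. At 1% it is at most about 0.4 points. These figures rest on the assumed log SD of 0.4, correlations of 0.6 to 0.9, log-normality and a stable untreated group. None of them is a document figure.

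A reader might infer that the SAP understates biomarker reductions in treated participants. The documents do not support that as a fact. They establish neither a below-LOQ rate nor a reduction persisting off drug, and the rule shrinks increases as well as reductions. This is a worthwhile correction to an exploratory analysis and does not bear on any primary or secondary endpoint.

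**What to change.** - **SAP 8.3:** reserve the missing category for samples not collected or invalid. State the LLOQ of each assay, and report below-LOQ counts by marker, group and visit.
- **SAP 8.8:** analyse below-LOQ post-baseline values as left-censored at the LLOQ in a log-scale censored-normal (Tobit) ANCOVA with the planned covariates, at least as a sensitivity analysis. State that participants with a below-LOQ baseline are excluded from this model and counted.
- **Do not substitute LLOQ/2.** In these scenarios it overstates a real reduction. At correlations of 0.8 and 0.9 its error is larger than that of the current rule; at 0.6 the two errors are of similar size and opposite sign.

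The cost is a few SAP sentences, one count table and one extra standard model, with no new data. The downside is reliance on log-normality below the limit, for an exploratory endpoint. If the counts show no below-LOQ results, the added model changes nothing.
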